14 EFFICACY ANALYSES

14.1 Efficacy Endpoints

14.1.1 Primary Efficacy Endpoint

The primary efficacy endpoint is having a change from baseline in blood bicarbonate ≥ 4 mEq/L or having a blood bicarbonate level in the normal range (22 to 29 mEq/L) at the end of treatment (Week 12 Visit). This outcome is termed “response”.

14.1.2 Secondary Efficacy Endpoint

The secondary efficacy endpoint is CFB in blood bicarbonate at the end of treatment (Week 12 Visit).

14.1.3 Exploratory Efficacy Endpoints

The exploratory efficacy endpoints identified in the study protocol are:

1. CFB in the total score of the Kidney Disease and Quality of Life (KDQOL) Question 3 items (daily activities) at the end of treatment (Week 12 Visit)
2. CFB in repeated chair stand test duration at the end of treatment (Week 12 Visit)

Additional exploratory efficacy endpoints (not specified in the study protocol) include:

1. CFB in parathyroid hormone (PTH)
2. CFB in serum pre-albumin
3. CFB in 25-hydroxy-vitamin D
4. CFB in urinary biomarkers of bone resorption:
 - a. N-terminal telopeptide (NTX)
 - b. C-terminal telopeptide (CTX)
5. CFB in serum biomarkers of bone resorption:
 - a. Tartrate-resistant acid phosphatase 5b (TRAP 5b)
 - b. Bone-specific alkaline phosphatase (BSAP)
 - c. Type 1 procollagen (P1NP)
6. CFB in urine renal biomarkers:
 - a. Urine angiotensinogen to creatinine ratio (UAGT)
 - b. Urine aldosterone
 - c. Uric acid
 - d. Sulfate
 - e. Urine endothelin-1 (ET-1)
7. CFB in serum osteocalcin (biomarker of bone formation)

If any biomarker samples have not been analyzed by the time of database lock, these assessments will be deferred and samples analyzed with those from the TRCA-301E study.

14.2 Efficacy Variables

14.2.1 Change from Baseline in Blood Bicarbonate

Blood bicarbonate values will be measured onsite using an i-STAT point-of-care device. Change from baseline in blood bicarbonate will be calculated as the measured value minus the baseline

value (see definition in Section 10.1.7) subsequent to the first dose of study drug. In other words, a positive change will indicate an increase in blood bicarbonate relative to baseline.

14.2.2 Categorical Change in Blood Bicarbonate

Binary indicator variables will be used to identify the frequencies of increases in post-baseline blood bicarbonate levels at each time point. The categories for the primary efficacy analysis are:

- an increase in blood bicarbonate from baseline ≥ 4 mEq/L
- blood bicarbonate value within 22 to 29 mEq/L

As additional exploratory efficacy analyses, the following categories will be evaluated:

- an increase in blood bicarbonate from baseline ≥ 2 mEq/L
- an increase in blood bicarbonate from baseline ≥ 3 mEq/L
- an increase in blood bicarbonate from baseline ≥ 5 mEq/L
- an increase in blood bicarbonate from baseline ≥ 6 mEq/L
- an increase in blood bicarbonate from baseline ≥ 7 mEq/L

14.2.3 Additional Change from Baseline Variables

As exploratory and other efficacy analyses, the following change from baseline variables will be calculated as the measured value minus the baseline value subsequent to the first dose of study drug. They will be measured once at baseline and once post baseline.

- CFB in the total score of the KDQOL Question 3 items (daily activities)
- CFB in repeated chair stand test duration
- CFB in parathyroid hormone
- CFB in serum pre-albumin
- CFB in 25-hydroxy-vitamin D
- CFB in urinary biomarkers of bone resorption (NTX and CTX)
- CFB in serum biomarkers of bone resorption (TRAP 5b, BSAP, and P1NP)
- CFB in urine renal biomarkers (UAGT, aldosterone, and ET-1)
- CFB in serum osteocalcin

14.3 Primary Efficacy Analysis

The primary analysis will be performed on the MITT analysis set, with the PP analysis set as supportive.

14.3.1 Reporting Results

The number and proportions (expressed as percentages) of subjects who are responders at each time point and at the end of treatment will be calculated. A responder is defined as a subject who has a change from baseline in blood bicarbonate ≥ 4 mEq/L or has a blood bicarbonate in the normal range (22 to 29 mEq/L). The difference in proportion of responders between TRC101 and placebo subjects and its two-sided exact (Clopper Pearson) 95% CI, as well as the p-value from Fisher's exact test comparing the TRC101 group and the placebo group, will be reported by time point. The exact 95% CIs will also be presented by treatment group and time point.

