This protocol allows the use of “background” medications that can affect eGFR and blood bicarbonate (e.g., oral alkali, calcium supplements, diuretics, renin angiotensin aldosterone system [RAAS] inhibitors) with some restrictions. Doses of alkali medications may not be changed and new oral alkali therapies must not be initiated during the study. If a subject requires treatment for sustained, clinically-significant worsening of metabolic acidosis during the study in the judgment of the Investigator, diet counseling (i.e., reduced protein intake, vegetarian/vegan protein sources) may be implemented as clinically appropriate and in agreement with the Medical Monitor. Subjects with confirmed blood bicarbonate decrease < 12 mEq/L should be investigated for possible causes of acute-on-chronic acidosis and the Investigator should discuss these cases with the Medical Monitor. The rationale for allowance of alkali treatment is to avoid significantly worsening acidosis among the placebo subjects; however, maintaining a stable dose of such treatments is necessary to avoid confounding of the primary efficacy measurement. Subjects may be, but are not required to be, on RAAS inhibitor(s) at Baseline. Investigators will be advised to avoid changing RAAS inhibitor doses during the study, when possible, but dose changes necessary for the management of comorbidities or acute events (e.g., hyperkalemia/worsening hyperkalemia) are not prohibited. Investigators will be advised to avoid changing diuretic doses when possible, but dose changes necessary for the management of comorbidities or acute events (e.g., heart failure, acute kidney injury) are not prohibited.

The rationale for the above restriction on background concomitant medications that may affect eGFR in this study is to gain experience with this aspect of the study design which may be used in a future study evaluating the rate of eGFR decline.

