4.4 Subject Withdrawal

Within the provisions of informed consent and good clinical judgment with respect to the subject’s safety, every attempt should be made to have subjects complete both the Treatment Period and Follow-up Period. All subjects will be informed that they have the right to withdraw from the study at any time. If a subject discontinues from the study prematurely the reason given must be fully evaluated and recorded appropriately in source documents and the electronic case report form (eCRF). Subjects withdrawn from the study prematurely will be followed for safety for 2 weeks after receiving the last dose of study drug. If the subject is being withdrawn because of an AE, that AE should be indicated as the reason for withdrawal. The Investigator and the Medical Monitor may exercise his or her medical judgment to discontinue a subject’s participation in the study at any time if medically necessary.

Subjects who meet any of the following criteria at any time during the study must be withdrawn from the study and should be medically managed as per standard of care by the Investigator:

- Occurrence of any AE, intercurrent illness or abnormality in laboratory assessment results which, in the opinion of the Investigator or Medical Monitor, warrants the subject’s permanent discontinuation of the study drug treatment.
- Treatment with a prohibited concomitant medication. Subjects who require a prohibited concomitant medication for the treatment of an AE or for a short duration may continue on study drug treatment if approved by the Medical Monitor (see [Section 5.9](#) for details).

- Subject's noncompliance, defined as refusal or inability to adhere to the study schedule, study drug self-administration or procedures, that cannot be rectified through additional training or other means.
- At the request of Tricida, IRB/IEC or regulatory authority.
- Withdrawal of consent by subject to participate in the study. Subjects should be encouraged to complete an Early Termination Visit, even if they are withdrawing consent, to ensure adequate safety follow-up.
- Subject is lost to follow-up (the subject did not return for visits and study personnel were unable to contact the subject after at least three documented attempts).
- Received dialysis or underwent renal transplantation.
- Pregnancy. These subjects will be followed until the outcome of pregnancy is known and if subject agrees (see [Section 6.12](#)).

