Note: If a dose change or addition or discontinuation of prohibited or restricted drug(s) is unavoidable for clinical management of the subject, contact a Medical Monitor for approval unless medical urgency precludes this. In all cases, notify a Medical Monitor within 24 hours of the change. "Stable dose" is defined as no starting or stopping of these medications and no change in dose. For diuretics, dose changes of up to \pm 50% relative to the average dose during the Screening Period are considered "stable". A dose change up to \pm 50% between the Screening 1 Visit and the Baseline Visit is considered "stable".

^a Short-term treatment (up to 4 days on up to 2 separate occasions) is allowed during the study for treatment of hyperkalemia in consultation with the Medical Monitor. Dose separation window of at least 4 hours from study drug required in these instances.

^b Lanthanum carbonate, colesevelam, colestyramine or sodium or calcium polystyrene sulfonate, calcium acetate, sevelamer, bixalomer, and other polymeric drugs.

^c Examples of carbonic anhydrase inhibitors include acetazolamide, methazolamide, dorzolamide, brinzolamide, zonisamide, topiramate, dichlorphenamide.

^d Antacid medications include milk of magnesia, proton pump inhibitors (e.g., omeprazole, pantoprazole, esomeprazole, lansoprazole), and H2 receptor antagonists (e.g., cimetidine, ranitidine, famotidine). Calcium supplements (e.g., calcium carbonate, calcium citrate, calcium chloride).

^e Examples of RAAS inhibitors: lisinopril, enalapril, perindopril, losartan, valsartan, candesartan, spironolactone, eplerenone.

^f Examples of diuretic drugs: furosemide, torsemide, hydrochlorthiazide, metolazone.

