13.2 Restricted Medications

The concomitant use of restricted medications as defined in the Study TRCA-301 protocol, Section 5.9 Table 1 will be summarized and listed separately, using the same dictionary mapping as described above or based on manual medical review. Number (%) of subjects who used new or changed dose of oral alkali and calcium supplements will be summarized. Summary of certain new/dose changed antihypertensive medications given systemically (i.e., diuretics and renin-angiotensin-aldosterone system [RAAS] inhibitors, such as angiotensin-converting enzyme [ACE] inhibitors, angiotensin II receptor blockers [ARBs], aldosterone antagonists [AAs], renin inhibitors, mineralocorticoid receptor antagonists [MRAs], β -blockers, calcium channel blockers, alpha-adrenergic antagonists drugs, and direct vasodilators) regardless of stated indication will also be provided. Calcium supplements are defined as orally administered calcium carbonate, calcium acetate, calcium citrate, and other calcium salts taken for any indication.

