14.3.2 Statistical Hypotheses

The two hypothesis tests will be used to evaluate the primary efficacy endpoint:

1. The null hypothesis is that there is no difference between treatment groups in proportion of subjects who are responders at Week 12. The alternative hypothesis is that there is a difference between treatment groups in proportion at Week 12

$$\begin{aligned} H_0: \pi_{\text{TRC101}} - \pi_{\text{placebo}} &= 0; \\ H_1: \pi_{\text{TRC101}} - \pi_{\text{placebo}} &\neq 0. \end{aligned}$$

2. The null hypothesis is that the proportion of TRC101 treated subjects who are responders at Week 12 is less than or equal to U (0.35 or 35%). The alternative hypothesis is that the TRC101 proportion at Week 12 is greater than U.

$$\begin{aligned} H_0: \pi_{\text{TRC101}} &\leq U; \\ H_1: \pi_{\text{TRC101}} &> U. \end{aligned}$$

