14.3.3 Statistical Testing

Statistical testing for the above hypotheses will be performed in the following sequence. The first formal test for the difference (TRC101 – placebo) in proportion ($\neq 0$) will be conducted at the Week 12 Visit using the Fisher's exact test. With successful rejection of the null hypothesis #1 (Section 14.3.2), the second formal test for TRC101 proportion ≤ 0.35 will be conducted at the Week 12 visit, using the two-sided 95% confidence lower limit. If the lower limit of the 95% CI for TRC101 treated subjects is above U (0.35 or 35%), the null hypothesis #2 (Section 14.3.2) will be rejected.

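### A Week 12 bicarbonate obtained on new or increased alkali counts as a response, and the single-arm 35% test has no control group to offset it

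*SAP*

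**What the plan says.** - **Responder rule.** SAP 14.3.1: "A responder is defined as a subject who has a change from baseline in blood bicarbonate ≥ 4 mEq/L", or who is in the 22 to 29 mEq/L range. SAP 14.1.1 fixes the time as Week 12. Neither section refers to alkali or dialysis. The primary analysis uses the MITT set (SAP 14.3).
- **Hypothesis #2.** SAP 14.3.2 and 14.3.3 test the TRC101 proportion against 35% "using the two-sided 95% confidence lower limit". The decision rule reads: "If the lower limit of the 95% CI for TRC101 treated subjects is above U (0.35 or 35%), the null hypothesis #2" is rejected. Placebo data do not enter.
- **Alkali as a confounder.** Protocol 1.6 allows background alkali but says that "maintaining a stable dose of such treatments is necessary to avoid confounding of the primary efficacy measurement".
- **The bar and its exceptions.** Protocol 5.9 and 5.10.3 forbid alkali changes and new oral alkali. The note under Protocol Table 1 then provides for the case "If a dose change or addition or discontinuation of prohibited or restricted drug(s) is unavoidable for clinical management of the subject", with Medical Monitor approval, or notification afterwards if urgent. Protocol 4.4 lets a subject who needs a prohibited drug for an adverse event, or briefly, stay on study drug if approved.
- **What the SAP does with such cases.** SAP 13.2: "Number (%) of subjects who used new or changed dose of oral alkali and calcium supplements will be summarized". SAP 12.2 lists restricted medications as a deviation category, and important deviations are excluded from the supportive per-protocol set (SAP 9.2). The only sensitivity analysis (SAP 14.5) concerns missing data.
- **Dialysis.** "Received dialysis or underwent renal transplantation" is a withdrawal criterion (Protocol 4.4).

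**The concern.** A subject whose alkali is started or increased with approval can remain to Week 12 and be scored on a value that alkali helped to raise. The MITT analysis counts that as a TRC101 response.

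In hypothesis #1 the placebo arm is open to the same thing. If placebo subjects need alkali more often, which is plausible but not stated, the bias runs against TRC101. Hypothesis #2 has no such counterweight: each added response can only push the TRC101 count towards the threshold. It is a formal test of the primary endpoint, so a count that includes responses to another bicarbonate-raising treatment weakens what a success would mean.

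**Working it through.** **Inputs.** 120 TRC101 subjects and at most 5% missing at Week 12 (SAP 8.1), so 120 × 0.95 = 114 evaluable. Threshold U = 0.35, lower limit of a two-sided 95% interval (SAP 14.3.3), exact type (SAP 14.3.1), hence a nominal one-sided 2.5%. Planned TRC101 rate 50% (SAP 8.1). The number of affected subjects, k, is not in the documents; I show small values as an assumption.

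**1. The plan's own figure.** At n = 114 the exact lower limit is 34.6% with 50 responders and 35.4% with 51, so success needs 51. Power at a true 50% is P(Bin(114, 0.50) ≥ 51) = 88.8%. At n = 120, 53 are needed and power is 91.5%. The SAP's roughly 90% is reproduced.

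**2. Error rate with no affected subject.** P(Bin(114, 0.35) ≥ 51) = 1.99%.

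**3. Error rate with k affected subjects, true rate 35%.** Two cases:
- *Otherwise non-responders:* k subjects who would have failed are scored as responders, P(Bin(n, 0.35) ≥ r − k), where r is the number needed.
- *Typical:* k subjects with a 35% chance of responding anyway are scored as responders, P(Bin(n − k, 0.35) ≥ r − k).

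| n (r) | k = 0 | Otherwise non-responder, k = 1 | k = 2 | Typical, k = 1 | k = 2 |
|---|---|---|---|---|---|
| 114 (51) | 1.99% | 3.11% | 4.71% | 2.62% | 3.42% |
| 118 (53) | 1.65% | 2.58% | 3.93% | 2.17% | 2.84% |
| 120 (53) | 2.35% | 3.59% | 5.33% | 3.06% | 3.93% |

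In the first case one subject takes the error above 2.5% at every n from 105 to 128. In the typical case it depends on n.

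**4. Does the preceding Fisher test protect?** No. With 114 and 86 evaluable, placebo at 10% and both tests required, the error is still 1.99% with none and 3.11% with one otherwise non-responder.

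**5. How local is the excess?** At n = 114 with one otherwise non-responder converted, the error is 2.4% at a true 34.5% and 1.8% at a true 34%.

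**6. At the planned rate.** About 57 of 114 responders are expected against 51 needed. One converted subject decides the outcome only if exactly 50 would otherwise respond: P(Bin(114, 0.50) = 50) = 3.2%.

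**7. After counting affected subjects as non-responders (n = 114).** Error at 35%, P(Bin(114 − k, 0.35) ≥ 51): 1.66% with one, 1.37% with two. Power at 50%: 87.1% with one, 85.1% with two.

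**The case against.** The strongest reply is that no error rate is lost. Hypothesis #2 concerns the proportion meeting a rule on the measured value, and for that quantity the test keeps its size. The excess exists only if response without added alkali is the target. This stands as a condition on the point. The SAP does not say which is meant, and Protocol 1.6 leans towards the second reading.

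Other replies that stand in part:
- **Rarity.** Alkali changes are barred, worsening acidosis is to be met with diet counselling, and prohibited medication leads to withdrawal unless approved. A reader might take the SAP 13.2 table as a sign that changes are expected. It is not: SAP 11.4.2 says alkali is monitored because the dose should not change.
- **Weak effect of alkali.** Protocol 1.1 reports only 2 to 3 mEq/L from oral sodium bicarbonate below 2 g a day. Alkali alone would often not reach +4, though it could carry a partial TRC101 response over the line.
- **Per-protocol set.** It may remove these subjects, but it is supportive, and what counts as important is left to a separate memo.

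A reader might also infer that any single such subject breaks the 2.5% level. The documents do not support that as a general statement: a typical subject at n = 118 leaves it at 2.17%. Nor is dialysis an equal route. It forces withdrawal, renal replacement planned within 12 weeks of randomization is an exclusion, and a later value counts as Week 12 only if drawn on Day 79 to 90 (SAP 10.2). Otherwise Week 12 is missing and is not imputed (SAP 11.3).

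**Conclusion.** The gap is real and modest. The MITT responder rule has no provision for a Week 12 value obtained on new or increased alkali, and hypothesis #2 has no control arm to offset it. At n = 114 and a true 35%, the exact error moves from 2.0% to between 2.6% (typical subject) and 3.1% (otherwise certain non-responder) with one affected subject, and to between 3.4% and 4.7% with two.

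This rests on three assumptions: the target is response without added alkali, the true rate is at or very near 35%, and at least one such subject occurs. The documents settle none of them. Alkali carries the point, with dialysis a minor addition. It should be clarified before unblinding; it does not show that the primary result would be wrong at the planned response rate.

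**What to change.** Keep the single responder definition. Add to SAP 14.3 an analysis, applied identically in both arms and to both hypotheses, that classes as a non-responder any subject whose Week 12 value was obtained while on alkali started or increased since baseline, or after dialysis. Tying the rule to treatment at the Week 12 draw avoids failing a subject for a brief, long-finished course. Require hypothesis #2 to be reported under this rule beside the as-observed result, and state which of the two quantities it is meant to test. Add one MMRM run for the secondary endpoint with bicarbonate values under these conditions set to missing.

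The cost is SAP wording and one flag from concomitant-medication and withdrawal data already collected. No trial procedure changes. The TRC101 responder count, and with it power for hypothesis #2 under the added rule, may be slightly lower: 88.8% to 87.1% with one affected subject at n = 114 and a true 50%.

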14.3.2 Statistical Hypotheses

The two hypothesis tests will be used to evaluate the primary efficacy endpoint:

1. The null hypothesis is that there is no difference between treatment groups in proportion of subjects who are responders at Week 12. The alternative hypothesis is that there is a difference between treatment groups in proportion at Week 12

$$\begin{aligned} H_0: \pi_{\text{TRC101}} - \pi_{\text{placebo}} &= 0; \\ H_1: \pi_{\text{TRC101}} - \pi_{\text{placebo}} &\neq 0. \end{aligned}$$

2. The null hypothesis is that the proportion of TRC101 treated subjects who are responders at Week 12 is less than or equal to U (0.35 or 35%). The alternative hypothesis is that the TRC101 proportion at Week 12 is greater than U.

$$\begin{aligned} H_0: \pi_{\text{TRC101}} &\leq U; \\ H_1: \pi_{\text{TRC101}} &> U. \end{aligned}$$

14.3.3 Statistical Testing

Statistical testing for the above hypotheses will be performed in the following sequence. The first formal test for the difference (TRC101 – placebo) in proportion ($\neq 0$) will be conducted at the Week 12 Visit using the Fisher's exact test. With successful rejection of the null hypothesis #1 (Section 14.3.2), the second formal test for TRC101 proportion ≤ 0.35 will be conducted at the Week 12 visit, using the two-sided 95% confidence lower limit. If the lower limit of the 95% CI for TRC101 treated subjects is above U (0.35 or 35%), the null hypothesis #2 (Section 14.3.2) will be rejected.

14.4 Secondary Efficacy Analysis

The secondary analysis will be performed on the MITT analysis set, with the PP analysis set as supportive. All scheduled blood bicarbonate values collected through the Week 12 visit will contribute to the analysis. The efficacy variable, the change from baseline in blood bicarbonate value, will be calculated for each time point after the first dose through the Week 12 visit (i.e., Weeks 1, 2, ..., 12). Missing data will not be imputed for the main analysis but will be imputed for the sensitivity analysis (Section 14.5). The analysis will test the difference in LS means between TRC101 and placebo at Week 12.

14.4.1 Statistical Hypothesis

For the secondary efficacy endpoint (i.e., the CFB in blood bicarbonate at Week 12 comparing TRC101 with placebo), the null hypothesis is the two means of CFB in blood bicarbonate are equal ($\mu_{\text{TRC101}} = \mu_{\text{placebo}}$). The alternative hypothesis is the two means of CFB in blood bicarbonate are not equal ($\mu_{\text{TRC101}} \neq \mu_{\text{placebo}}$).

14.4.2 Statistical Model

The MMRM model will define the CFB in blood bicarbonate as the dependent variable, set treatment, time point, and treatment by time point interaction as fixed effects, subject as a random effect, and the baseline eGFR and baseline blood bicarbonate as continuous covariates. Within-subject correlations will be modeled using an unstructured covariance structure. Time ordering is a repeated measure within subjects. Errors for different subjects are assumed independent with an unstructured covariance structure. The estimation method for the model will be restricted maximum likelihood (REML).

In the event the MMRM model with an unstructured covariance structure does not converge, the following covariance structures will be used as substitution in the order below. Each subsequent covariance structure will be used only if each previous covariance structure was used and the model did not converge.

1. Toeplitz covariance structure (assuming measurements from samples taken closer together in time are more highly correlated than those from samples taken farther apart)

2. First order of auto-regressive [AR(1)] covariance structure (assuming measurements from samples taken closer together in time are more highly correlated than those from samples taken farther apart)
3. Compound symmetry covariance structure (assuming equal correlation for measurements from a subject, regardless of how far apart in time when they were taken)

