8.5.3.2 Secondary Efficacy Analyses

The secondary efficacy analysis will compare the TRC101 group with the placebo group in LS mean CFB in blood bicarbonate at the end of treatment (Week 12 Visit). The null hypothesis is that there is no mean difference between the TRC101 group and the placebo group. The alternative hypothesis is that the means differ. The secondary efficacy endpoint will be assessed using a longitudinal mixed-effect model for repeated measures (MMRM). The model will include the CFB in bicarbonate as the dependent variable, treatment, time point (Weeks 1, 2, ..., 12), and treatment by time point interaction as fixed effects, subject as a random effect, the baseline bicarbonate and baseline eGFR as continuous covariates. An unstructured covariance structure will be assumed. The least squares (LS) mean of CFB in bicarbonate, standard error of LS mean, and two-sided 95% CIs of the LS mean from the mixed model will be reported by time point and treatment group. The LS mean difference from placebo (i.e., TRC101 – placebo), SE of the LS mean difference, 95% CIs of the LS mean difference, and p-values of the LS mean difference from the mixed model will be reported by time point. Only when the primary efficacy endpoint is statistically significant will formal testing be performed for the secondary efficacy endpoint. Meeting the secondary endpoint will be declared if the two-sided p-value at Week 12 is <0.05 and the primary efficacy endpoint is statistically significant.

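### The secondary-endpoint MMRM combines a random subject effect with an unstructured covariance, which is not identifiable; a failed fit would send the analysis to equal-variance fallbacks that misstate the Week 12 interval if variance changes over visits

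*SAP*

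**What the plan says.** SAP 14.4.2 defines the MMRM for the secondary endpoint, change from baseline in blood bicarbonate at Week 12. Treatment, time point and their interaction are fixed effects, with "subject as a random effect, and the baseline eGFR and baseline blood bicarbonate as continuous covariates". It then states: "Within-subject correlations will be modeled using an unstructured covariance structure". A further sentence puts the same structure on the residuals: "Errors for different subjects are assumed independent with an unstructured covariance structure". Estimation is by REML.

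Protocol 8.5.3.2 has the same combination: "subject as a random effect, the baseline bicarbonate and baseline eGFR as continuous covariates", followed by "An unstructured covariance structure will be assumed".

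If the unstructured model does not converge, the SAP says "the following covariance structures will be used as substitution in the order below": Toeplitz, then AR(1), then compound symmetry. The rule is strictly sequential: "Each subsequent covariance structure will be used only if each previous covariance structure was used and the model did not converge". It does not say to drop the random effect before changing structure. No heterogeneous-variance version, robust standard error or degrees-of-freedom method is named.

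For planning, SAP 8.2 assumes a constant SD of 3.0 mEq/L at all seven post-baseline visits (Weeks 1, 2, 4, 6, 8, 10 and 12).

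**The concern.** An unstructured covariance leaves nothing for a random subject intercept to explain. If both terms are coded as written, the model has one parameter more than the data can identify. A convergence failure could then come from the specification and not from the data.

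This matters because convergence is the SAP's switch for choosing the covariance structure. A redundant term could set off a rule meant for data problems, and all three substitutes impose one common variance on every visit. The standard error and confidence interval for the Week 12 difference would then rest on that assumption. This is the only secondary endpoint and it is formally tested after the primary, so its covariance model should not depend on an avoidable redundancy.

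**Working it through.** **Planning figures (SAP 8.2).** The tabulated means average 0.55 (placebo) and 3.286 (TRC101), so the group variance is ((3.286 − 0.55)/2)² = 1.871, as stated. The mean off-diagonal correlation is 0.357. The error terms are therefore 3√(1 + 6 × 0.357) = 5.32 and 3√(1 − 0.357) = 2.41 (stated 5.32 and 2.4), and epsilon is 0.686 (stated 0.69). Power for the time effect at 104 per group is 85.9% (stated 85%); group and interaction power exceed 99%. The planning section reproduces, and it rests on constant SD.

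**Parameter count.** The marginal covariance is V = s·J + R, where s is the subject variance, J a matrix of ones and R the residual covariance. For 7 visits V has 7 × 8/2 = 28 distinct elements. The rank of the map from parameters to V is:

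| Residual structure | Parameters alone | With subject effect | Rank with subject effect | Identifiable with subject effect |
|---|---|---|---|---|
| Unstructured | 28 | 29 | 28 | No |
| Toeplitz | 7 | 8 | 7 | No |
| AR(1) | 2 | 3 | 3 | Yes |
| Compound symmetry | 2 | 3 | 2 | No |

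Without the subject effect, all four are identifiable.

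**Width of the flat ridge.** R = V − s·J stays positive definite for s below 1/(1′V⁻¹1). With V = 9C and C the SAP 8.2 correlation table, 1′C⁻¹1 = 2.345, so the bound is 9/2.345 = 3.84. At s = 0, 0.5, 1, 2 and 3, V and its log-determinant (12.684) are identical. The likelihood, LS means and standard errors therefore do not change along the ridge.

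**Effect of a common-variance fallback.** Inputs: 90 placebo and 120 TRC101 (SAP 8.1), complete data, no covariates, normal approximation.

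- True SE = SD at Week 12 × √(1/90 + 1/120) = SD at Week 12 × 0.1394.
- Fallback SE = root-mean-square SD over the 7 visits × 0.1394.
- Coverage = 2Φ(1.96 × ratio) − 1, where ratio = fallback SE / true SE.

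The SD is assumed to change linearly in weeks from Week 1 to Week 12. Apart from the constant 3.0, these patterns are assumptions. The documents give only 2.5 (the common SD in the two-week study) and 3.0 (planning).

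| SD, Week 1 to Week 12 | Pooled SD | Ratio | True SE | Fallback SE | Coverage |
|---|---|---|---|---|---|
| 3.0 constant (SAP) | 3.000 | 1.000 | 0.418 | 0.418 | 95.0% |
| 2.5 to 3.0 | 2.739 | 0.913 | 0.418 | 0.382 | 92.6% |
| 2.5 to 3.5 | 2.988 | 0.854 | 0.488 | 0.417 | 90.6% |
| 2.5 to 4.0 | 3.243 | 0.811 | 0.558 | 0.452 | 88.8% |
| 3.0 to 2.5 | 2.772 | 1.109 | 0.349 | 0.386 | 97.0% |
| 3.5 to 2.5 | 3.052 | 1.221 | 0.349 | 0.426 | 98.3% |

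For the rising patterns, the best-fitting Toeplitz gives almost the same coverage (92.7%, 90.7%, 88.9%), so pooling is a fair stand-in for the listed structures.

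**Significance.** The planned Week 12 difference is 4.25 − 0.25 = 4.0. With the largest true SE in the table, z = 4.0/0.558 = 7.2. No row brings the test near 0.05.

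**The case against.** The strongest reply is that the random effect is loose wording for subject as the clustering unit. SAP 14.4.2 also calls time a repeated measure within subject and puts the unstructured matrix on the errors, which describes an ordinary repeated-measures MMRM. No separate variance structure for the subject effect is given. This reading is plausible, but the text lists the random effect as a model term in its own right, and a programmer could code both.

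A second reply is that redundancy need not cause a fallback. This stands. The trigger is non-convergence, and the SAP does not say how to treat a singular Hessian or a subject variance set to zero. In six simulated trials built from the SAP's means and correlations (SD 3.0, 120 and 90 subjects, about 5% dropout, no covariates), the redundant model met a general-purpose optimiser's criterion in five and narrowly missed the gradient tolerance in the sixth. In all six, the Week 12 difference and SE agreed with the plain unstructured fit to about five decimals. That was not SAS, so it does not settle how SAS would behave, but it shows that failure is a risk and not a certainty.

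Third, a reader might infer that fallback intervals would be too narrow because titration makes the SD grow. The documents do not support a direction. The dose goes up below 22 mEq/L and down at 27 to 30 mEq/L (Protocol Appendix 2), which could compress the spread as easily as widen it. The 2.5 comes from a short inpatient study on a controlled diet, so comparing it with 3.0 is not evidence of growth within this trial.

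Unequal visit spacing is a lesser matter. Only the Week 1 to Week 2 gap differs from two weeks, and the SAP's planning table already gives it the same correlation, 0.6, as the later gaps.

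**Conclusion.** The specification is over-parameterised by exactly one parameter in both documents, and the first and third fallbacks inherit the fault if the subject effect stays in. This is algebra and needs no assumption about the data, provided the random effect is read literally.

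The consequence is conditional. It needs a failed fit and a variance that differs across visits. If both occur, Week 12 coverage is about 93% to 89% for an SD rising from 2.5 to 3.0–4.0, and about 97% to 98% for an SD falling from 3.0–3.5 to 2.5. At the SAP's constant SD of 3.0 there is no error.

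Two stronger readings should be resisted. The redundancy does not bias the treatment effect: in a converged fit the LS means and SEs are those of the plain unstructured model. Nor does the plan carry an inflated type I error. Rates of 7% to 11% (100% minus the coverage above) arise only if the fit fails and SD rises as assumed, and the test result at the planned effect would not change. What is at stake is the reported Week 12 interval and clean pre-specification. It is worth correcting because the correction is nearly free.

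**What to change.** 1. In SAP 14.4.2 and Protocol 8.5.3.2, delete the words that make subject a random effect. State instead that visit is the repeated factor within subject, with an unstructured covariance. This leaves the intended model and its inference unchanged.
2. Replace the fallbacks with heterogeneous Toeplitz, heterogeneous AR(1) and heterogeneous compound symmetry, in that order. Alternatively, keep the three listed structures and report empirical (sandwich) standard errors.

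The cost is a few sentences of text. Each heterogeneous fallback has 7 variances in place of 1, so six more parameters, which is a small drawback when the unstructured fit has already failed. The sandwich option avoids it. Naming a degrees-of-freedom method would be a useful optional addition, but Kenward-Roger should not be paired with sandwich standard errors in the same fallback.
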